**DESIGN: Randomized Control Trail**

**DATA COLLECTION PROCEDURE:**

After screening of more than 50 MI patients 26 stable post MI patients both males and females on the basis of inclusion and exclusion criteria were enrolled. After enrollment final step for inclusion in study was 6 minute walk test. All patients performed treadmill 6 minute walk test. Patients that successfully completed initial 3 min of walk test were included in the study. Informed consent was signed by all patients as an agreement to participate in research. Total patients at end of study was 26 with drop outs of 4 .After enrollment in study 1st day was pre assessment day.1st step was selection in either control or experimental group. Lottery method was used for random allocation of patients. Self structured questionnaire was filled that included demographics, patient past medical, surgical, drug history, comorbidites, risk stratification. Basic baseline evaluation was done that included ECG, urea, creatinine, lipid profile. Pre echocardiography of all patients was done Pre MAC New QLMI was filled by examiner herself. After completion of all pre assessment exercise session of the patient was started from next session. Total weeks of treatment session were 6. Exercise was performed 3 times a week on alternating days. Total days of exercise were 18. Before treatment session proper warm up for 15 minutes was done Pre vitals including heart rate, BP, Respiratory rate, SpO2 was recorded. Karvonens formula was used to calculate 60-80% of target heart rate in all patients .The goal of exercise was to reach target heart rate. Emergency trolley consisting of major life saving drugs was available that included (Angisid, Injection Atropine, Adrenaline, Heparin, Lignocaine, Streptokinase, Nitroglycin, Normal Saline, Glucose) plus examiner was qualified in ACLS. Patient speed was increased gradually from first to six weeks depending on each patient target heart rate. Likewise weight in quadriceps resistive exercise and hand grippers were increased gradually with number of repetitions remaining same. Rating of perceived exertion and fatigue scale was used to mark patient dyspnea and fatigue level. Patients in control group were given standard aerobic interval treatment while patient in experimental group was given aerobic plus resistance interval treatment. During session continuous vital monitoring was done using saturation probe and cardiac monitor. After completion of session post vitals HR, BP, RR, Spo2 RPE and fatigue Cool down exercises were performed to stabilize patient. After completion of total 6 weeks of intervention patients post tests were done that included Echocardiography, lipid profile post and Mac New QLMI.

[figure not shown]

Figure 2: Flow chart showing Data collection procedure

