## DATA ANALYSIS PROCEDURE:

All the patients were assessed at the baseline before the intervention and at the completion of the study. Data was analyzed by using IBM SPSS 21 (Statistical Package for Social Sciences) and expressed in the form of tables and graphs.

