## CURVES OF NORMALITY

[figure not shown]

Figure 4: Normality test (histograms) for Baseline Vitals, A: Heart rate, B: Respiratory rate, C: Saturation, D: Systolic BP, E: Diastolic BP

We applied normality test on Baseline vitals. Histogram showed abnormally skewed curves for Heart rate, respiratory rate and oxygen saturation ( $p=0.000, 0.030, 0.004$ ) respectively and normally skewed curves for systolic and diastolic BP ( $p=0.396$  and  $0.108$ ) respectively. Test of choice is non-parametric, Mann-Whitney U test for the comparison between groups (sample size  $< 30$  in each group).

[figure not shown]

Figure 5: Normality test (histograms), A: Ejection Fraction

We applied normality test on baseline ejection fraction. Histogram showed abnormally skewed curve for ejection fraction ( $p=0.001$ ). Test of choice is non-parametric, Mann-Whitney U test for the comparison between groups (sample size  $< 30$  in each group.)

[figure not shown]

Figure 6: Normality test (histograms), A: Cholesterol, B: Triglycerides

We applied normality test on baseline cholesterol and triglycerides. Histogram showed abnormally skewed curves for cholesterol and triglycerides ( $p=0.000, 0.026$  respectively). Test of choice is non-parametric, Mann-Whitney U test for the comparison between groups (sample size  $< 30$  in each group)

[figure not shown]

Figure 7: Normality test (histograms) for Baseline Quality of life, A: Emotional state, B: Physical state, C: Social state

We applied normality test on baseline quality of life including its three domains of emotional, physical and social state. Histogram showed abnormally skewed curve for emotional ( $p=0.025$ ) and normally skewed curves for physical and social state ( $p=0.129$  and  $0.577$  respectively). Test of choice is non-parametric, Mann-Whitney U test for the comparison between groups (sample size  $< 30$  in each group.)

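### Lots are drawn before the examiner-filled baseline MacNew, with no masking or concealment described, so subjective baseline scores are open to influence from known allocation

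*Combined protocol and SAP*

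**What the plan says.** DATA COLLECTION PROCEDURE takes the pre-assessment day in this order.

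- Allocation: "1st step was selection in either control or experimental group", with lots as the method. Who drew them, and whether they were concealed, is not described.
- Baseline work, described next: a questionnaire, ECG and blood tests, echocardiography, then the MacNew form, of which it says "Pre MAC New QLMI was filled by examiner herself".
- Start of treatment: "After completion of all pre assessment exercise session of the patient was started from next session".

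After six weeks, "patients post tests were done that included Echocardiography, lipid profile post and Mac New QLMI". The text does not say who recorded the second MacNew. DATA ANALYSIS PROCEDURE confirms two assessment times: "All the patients were assessed at the baseline before the intervention and at the completion of the study". For quality of life, CURVES OF NORMALITY says "Test of choice is non-parametric, Mann-Whitney U test for the comparison between groups", without stating whether the test is applied to post-treatment values or to change.

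No supplied section mentions masking of the examiner, the patients or the outcome assessors. Two sources are unavailable: the chart captioned "Figure 2: Flow chart showing Data collection procedure" is not shown, and some material was removed before review.

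**The concern.** A baseline outcome is protected from the allocation if it is recorded before the draw, or by someone who does not know the result. The order described gives up the first protection, and nothing described supplies the second.

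This matters most for MacNew. Its emotional, physical and social domains are subjective, and someone other than the patient filled in the form. Laboratory results are less exposed. If answers were recorded differently by arm, the baseline scores could differ with no true difference between the groups. A change score subtracts that artefact from the outcome, a baseline-adjusted analysis carries part of it, and a statement that the groups were balanced at baseline would rest on a contaminated measure.

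Nothing described for that day needs the group to be known, because exercise starts only at the following session.

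**Working it through.** **Order of events.** The place of the lottery is explicit, since it is called the first step. The place of MacNew is read from narrative order, which is weaker evidence: the same paragraph gives end-of-study totals before it describes the first day. All pre-assessment ends before the first exercise session, so the draw could move to the end of that day without delaying treatment.

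**Illustration of size.** The plan gives no figure to reproduce. Everything below except the patient counts is assumed.

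- Patients per arm: the protocol says "Total patients at end of study was 26 with drop outs of 4", which can be read in several ways. Equal arms give 22/2 = 11, 26/2 = 13, or (26 + 4)/2 = 15 at baseline. The split is not stated.
- Scores: SD 1 at both visits, correlation r of 0.3, 0.5 or 0.7, no true effect.
- Bias: a shift s in one arm's baseline only.
- Test: two-sided Mann-Whitney at 0.05, by simulation (40,000 runs per cell).

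The SD of change is √(2(1 − r)), so s = 0.5 becomes a spurious standardised difference in change of:

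- r = 0.3: 0.5/√1.4 = 0.5/1.183 = 0.42
- r = 0.5: 0.5/√1.0 = 0.50
- r = 0.7: 0.5/√0.6 = 0.5/0.775 = 0.65

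False-positive rates per domain, normal data, s = 0.5:

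| Per arm | Change, r = 0.3 | Change, r = 0.5 | Change, r = 0.7 | Post values |
|---|---|---|---|---|
| 11 | 14.4% | 18.7% | 28.0% | 4-5% |
| 13 | 15.7% | 20.3% | 31.6% | 4-5% |

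Smaller baseline shifts do less: on change, 6-9% for 0.2 SD and 8-14% for 0.3 SD. With no shift, the rate on change is about 4-5%. Post values are unaffected because the shift never enters them.

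In a baseline-adjusted analysis (analysis of covariance) the spurious effect is r × s against a residual SD of √(1 − r²). That is 0.15/0.954 = 0.16 at r = 0.3 and 0.35/0.714 = 0.49 at r = 0.7. The simulated rates run from 6% to 21%.

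**Would a baseline comparison reveal the shift?** Often not. Mann-Whitney detects a 0.5 SD baseline shift this often (skewed data are standardised lognormal, sigma 0.6):

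| Per arm | Normal data | Skewed data |
|---|---|---|
| 11 to 13 | 19-21% | 31-37% |
| 15 | 24% | 41-42% |

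The skewed column is relevant because CURVES OF NORMALITY reports the emotional domain as skewed.

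**Does moving the draw suffice?** Only if upcoming lots cannot be foreseen. Suppose, as an assumption, a fixed pot of m lots per arm drawn without replacement. A person tracking the draws would guess correctly a share (m + 2^(2m−1)/C(2m, m) − 0.5)/(2m). For m = 13 this is (13 + 3.226 − 0.5)/26 = 60.5%, and for m = 15 it is (15 + 3.461 − 0.5)/30 = 59.9%.

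**The case against.** The case against has four parts.

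1. *The chain of harm is unproven.* The examiner must have known the group, influenced answers rather than written them down, and done so differently by arm, and the analysis must have used baseline. The documents establish none of these. The analysis text mentions no change score and no covariate, and a comparison of values at a visit is at least as natural a reading. This stands, and it makes the harm conditional. It does not remove the weakness in the order, which is stated and avoidable.

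2. *The sequence may be different.* The flow chart could settle it and is not shown. This stands for the place of MacNew but not for the lottery, so any limitation should be reported only after the sequence is confirmed.

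3. *Nothing can be re-ordered now.* The text is largely in the past tense and reports end-of-study numbers, so recruitment appears complete. This stands: the re-ordering helps only further recruitment or reuse.

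4. *The 6-week MacNew is a separate problem.* This also stands. Bias at follow-up does not come from the order of the draw, and re-ordering does not touch it.

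A reader might infer that the baseline scores were biased, that the examiner was unmasked, or that moving the draw alone would close the route. The documents support none of these. They are silent on what she knew and did, and closing the baseline route also needs concealed lots.

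**Conclusion.** The concern holds in conditional form. The draw is explicitly first, the examiner-filled baseline MacNew is described after it, and the supplied text offers neither masking nor concealment. That leaves a route by which known allocation could affect subjective baseline scores. It does not show that it did.

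If it did, change-score and baseline-adjusted comparisons and claims of baseline balance would be affected, and a comparison of post values alone would not be. For a 0.5 SD baseline-only shift with normal data and 11 to 13 per arm, the false-positive rate on change would be about 14-32%, against 4-5% on post values. A non-significant baseline comparison would give little reassurance, with detection of about 19-24% for normal and 31-42% for skewed data at 11 to 15 per arm. Shift, correlation, distribution and equal arms are assumptions, and the case for acting does not depend on them. It rests on the stated order and on how little it costs to change. Confidence is medium because the flow chart is unavailable.

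**What to change.** **For further recruitment or reuse of the protocol.** Draw concealed lots only after all baseline outcome measures are recorded. This needs no extra visit and no delay. The cost is preparing lots that staff cannot see or predict. It does not protect the 6-week MacNew, which needs its own safeguard.

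**For data already collected.**

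1. Confirm the sequence from the flow chart or study records, and state whether the examiner knew the group when the baseline MacNew was filled in.
2. If the form did follow allocation and she knew the group, report that as a limitation.
3. In that case, also state whether Mann-Whitney was applied to post values or to change. If change was used, show the post-value comparison as a supportive analysis. A baseline-only shift does not affect it, but it gives no protection against bias at follow-up.

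The cost is a few sentences and, if change was used, one further table. That table would take the three domain tests to six, so the second set should be labelled supportive.

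### Baseline ejection fraction is measured in every patient but, as described, is used neither in the allocation nor in the between-group test; the 6-week comparison should be adjusted for it.

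*Combined protocol and SAP*

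**What the plan says.** On allocation, the section DATA COLLECTION PROCEDURE says "Lottery method was used for random allocation of patients". It describes no stratification factor, block structure, allocation ratio or arm sizes. Group assignment opens the pre-assessment day ("1st step was selection in either control or experimental group"), and the baseline echocardiogram is described after it ("Pre echocardiography of all patients was done"). The same section lists echocardiography, the lipid profile and the MacNew questionnaire again after the six weeks of training.

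On analysis, the section CURVES OF NORMALITY reports for baseline ejection fraction that "Histogram showed abnormally skewed curve for ejection fraction" (p=0.001) and concludes "Test of choice is non-parametric, Mann-Whitney U test for the comparison between groups". The same conclusion follows for vitals, lipids and the quality-of-life domains. No covariate is mentioned, and the text does not say whether the test is run on 6-week values or on change from baseline.

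On numbers, 26 appears twice. It is the enrolled count ("After screening of more than 50 MI patients 26 stable post MI patients both males and females") and also the final count ("Total patients at end of study was 26 with drop outs of 4"). The number allocated could therefore be 26, leaving 22, or 30, leaving 26.

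**The concern.** With about 13 patients per arm, randomisation alone leaves sizeable chance differences at baseline. A patient's ejection fraction before training is likely to predict the value six weeks later, so part of any starting difference reappears at follow-up and can be mistaken for a training effect, or can hide one. A trial can guard against this by balancing the baseline value at allocation or by adjusting for it in the analysis. The documents describe neither, although the measurement is already made.

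Two things are at stake. One is how far a p-value can be trusted in a trial where the arms are visibly unequal at baseline. The other is precision, which a trial of this size can ill afford to lose.

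**Working it through.** The documents give no power or imbalance figure, so there is nothing of theirs to reproduce.

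**Inputs.** From the documents: 26 patients (with the ambiguity above), lottery allocation, Mann-Whitney U, and assessments at baseline and completion. Assumed, because not stated: 13 per arm (checked from 11 to 15), and a baseline/6-week correlation r of 0.5, 0.7 or 0.8 (checked from 0.3 to 0.9).

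**Step 1: chance of a baseline gap over 0.5 SD.** The standard error of the difference in baseline means, in SD units, is √(1/n₁ + 1/n₂), and P = 2 × [1 − Φ(0.5/SE)].

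- 13:13: SE = √(2/13) = 0.392; 0.5/0.392 = 1.275; P = 20.2%.
- 11:11: SE = √(2/11) = 0.426; P = 24.1%.
- 15:15: SE = √(2/15) = 0.365; P = 17.1%.
- Fully independent draws, averaging over the possible splits: 25.3% for 22 patients, 21.2% for 26, 17.9% for 30.
- Skewed instead of normal data at 13:13: 19% to 22%.

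Forcing equal arms changes the 26-patient figure only from 21.2% to 20.2%.

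**Step 2: how much of the gap carries over.** With no treatment effect, the expected 6-week gap is r times the baseline gap. On change scores it is −(1 − r) times the baseline gap, so it is partial and in the opposite direction. Among trials where the gap exceeds 0.5 SD it averages about 0.69 SD. At r = 0.7 that leaves about 0.7 × 0.69 = 0.48 SD on 6-week values, or −0.3 × 0.69 = −0.21 SD on change.

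**Step 3: error rates.** Simulation with no treatment effect, 13:13, normal data, two-sided 5% level, 100,000 trials per row. Rejection rates are for trials with a baseline gap over 0.5 SD, except the last column.

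| r | Mann-Whitney, 6-week values | Mann-Whitney, change | Rank ANCOVA | Mann-Whitney, 6-week values, gap of 0.5 SD or less |
|---|---|---|---|---|
| 0.5 | 9.4% | 9.3% | 5.4% | 3.2% |
| 0.7 | 13.9% | 7.6% | 5.4% | 1.9% |
| 0.8 | 16.7% | 6.7% | 5.5% | 1.3% |

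With left-skewed data (a log-normal shape, chosen as an assumption) the rates in gap trials are 8.2%, 12.2% and 14.7% on 6-week values, 9.0%, 7.3% and 6.6% on change, and 5.2% to 5.5% for rank ANCOVA. Over r = 0.3 to 0.9 with normal data, the unadjusted rate in gap trials runs from about 6% to 20% on 6-week values and from about 11% down to 5% on change.

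Averaged over all trials, the Mann-Whitney rate is 4.3% to 4.6%. For example, at r = 0.7: 0.20 × 13.9% + 0.80 × 1.9% = 4.3%.

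**Step 4: precision.** In SD units, the standard error of the treatment difference is 0.392 on 6-week values and 0.392 × √(2(1 − r)) on change. With linear baseline adjustment it is about 0.392 × √(1 − r²) × √(23/22), where the last factor is the cost of estimating the slope from 26 patients.

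| r | 6-week values | Change | Adjusted |
|---|---|---|---|
| 0.5 | 0.39 | 0.39 | 0.35 |
| 0.7 | 0.39 | 0.30 | 0.29 |
| 0.8 | 0.39 | 0.25 | 0.24 |

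**The case against.** The strongest reply is that a lottery followed by Mann-Whitney is a valid procedure. Its false-positive rate over all trials is slightly under 5%, and the high rates apply only to the unlucky fifth and are offset by low rates in the rest. That stands. This point concerns conditional error and lost precision, not a biased or invalid test.

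Several stronger readings are tempting, and the documents do not support them.

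- A reader might infer that the lottery was unrestricted and that this produces the 1-in-5 figure. The text is silent on restriction, a lottery can use equal numbers of slips, and the flow chart is not readable here. Equal arms would hardly change the figure in any case.
- A reader might infer that the baseline gap passes intact into the result. Only the fraction r does on 6-week values, and on change scores the effect is smaller at the higher correlations and reversed. The documents do not say which is tested. Each naming of the test follows a check of baseline data, so even its application to follow-up values is inferred.
- A reader might conclude that the lottery must be replaced by a list stratified on ejection fraction. With normal data split at the median, stratification would cut the 20% to about 6%. However, ejection fraction is reported as non-normal and no suitable cut-point can be read from the text. Assignment is also described before the echocardiogram, and much of the text reports enrolment and testing as already done.

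If change scores were intended, the loss is small at high correlations (0.25 against 0.24 at r = 0.8). That also stands, but nothing says they were.

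**Conclusion.** The point holds as a recommended improvement to the analysis, not as a flaw that invalidates the trial. As described, neither allocation nor comparison uses a baseline value that every patient has. The chance of a gap over 0.5 SD is about 20%, or 17% to 25% over the plausible numbers. In those trials the nominal 5% test on 6-week values behaves like one of roughly 8% to 17% for correlations of 0.5 to 0.8, and on change scores like one of roughly 6% to 10%. Compared with an unadjusted comparison of 6-week values, adjustment would shrink the standard error by about 11% to 39% (0.392 to 0.348 and 0.241).

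The imbalance figure rests on the assumed arm sizes. The error and precision figures also rest on the assumed correlation and distribution, none of which the documents give. At a correlation near 0.3 the precision gain on 6-week values is slight. Ejection fraction is used because it is the clearest case, and the reasoning applies equally to the other outcomes measured twice.

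**What to change.** State in the analysis section that the between-group comparison of 6-week ejection fraction is adjusted for its own baseline by rank-based ANCOVA. Rank the 6-week values across both groups, rank the baseline values likewise, regress the first on group and the second, and test the group term. This suits the reported skewness. Apply the same rule to each other outcome measured at baseline and six weeks, including lipids and the quality-of-life domains.

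Also state the number allocated to each arm and whether the lottery fixed the arm sizes, and reconcile the two uses of 26. If follow-up results have already been seen, report the adjusted analysis beside the unadjusted one and say when it was added.

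The cost is a few sentences and one model per outcome in the software already named, with no new visits, measurements or staff. Stratified allocation remains an optional choice for patients not yet allocated. It would require the echocardiogram to come before assignment, and an analysis that respects the strata.

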### **TREATMENT PROTOCOL:**

Patients in both group received standard treatment that is Aerobic Interval training whereas patients in interventional group was given Resistance Interval Training as well.

Before initiation of treatment protocol vitals (HR, BP, RR and SPO2) will be recorded. Treatment of both groups will start with 3-5 minutes of warm up that includes breathing exercises and stretching of major large muscles. Exercise will be performed at 60-80 % of intensity calculated by karvonen formula. Throughout training monitoring will be done.

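### The baseline MacNew is filled in by the examiner and no other method is given for week 6, so the 6-week quality-of-life scores may be recorded by someone who knows the arm

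*Combined protocol and SAP*

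**What the plan says.** All statements about who does what are in the Data Collection Procedure section.

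- **Allocation comes first.** On the pre-assessment day, "1st step was selection in either control or experimental group", and "Lottery method was used for random allocation of patients". The baseline tests follow.
- **Baseline MacNew.** "Pre MAC New QLMI was filled by examiner herself".
- **6-week MacNew.** After the intervention, "patients post tests were done that included Echocardiography, lipid profile post and Mac New QLMI". No person and no method is named.
- **Examiner and sessions.** The account of the emergency trolley ends with "plus examiner was qualified in ACLS".

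Elsewhere, the Treatment Protocol section says that "patients in interventional group was given Resistance Interval Training as well". The Curves of Normality section describes the outcome as "baseline quality of life including its three domains of emotional, physical and social state" and adds: "Test of choice is non-parametric, Mann-Whitney U test for the comparison between groups".

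The available text describes no blinded assessor, no independent assessor and no completion by the patient.

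**The concern.** The MacNew domains describe how the patient feels and functions. Unlike the lipid profile, they have no laboratory reading behind them, so the score depends on who asks, who interprets the reply and who marks the form.

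If an examiner who knows the arm does this at week 6, a between-group difference could come from the treatment, from the way answers were put and recorded, or from both. The analysis cannot separate them. One person would also record all three domains, so errors would tend to move together, and agreement across domains would not be independent confirmation.

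This is separate from the fact that allocation precedes baseline. Drawing the lottery after the baseline tests would protect the baseline scores. It would do nothing for the 6-week scores, where a treatment effect would appear.

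**Working it through.** **Step 1. What is stated and what is inferred**

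| Link | Status |
|---|---|
| Examiner fills in the baseline form | Stated |
| Allocation precedes the baseline form | Stated |
| Arms look different in a session | Follows from the group descriptions: only the interventional group uses hand grippers and biceps and quadriceps resistance |
| Examiner fills in the 6-week form | Not stated; inferred because no other method is given and pre and post scores should be collected alike |
| Examiner attends the sessions | Not stated; inferred because the ACLS qualification is given as part of the emergency cover |
| Examiner asks and rates, or only writes down the patient's answers | Not stated |

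If the inferences hold, the examiner could have watched up to 6 weeks × 3 sessions = 18 arm-specific sessions before the 6-week form. If the mode instead differed between visits, pre and post scores would not be collected alike, which is also a fault. Either way the plan has to state the 6-week mode.

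**Step 2. Illustration of sensitivity**

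The plan gives no power, alpha or effect size for the MacNew, so there is no figure to reproduce. The question is how far the planned test would react to a given shift.

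Inputs:
- Test: Mann-Whitney U (Curves of Normality).
- Alpha: 5% two-sided (assumed).
- Patients per arm: the split is not given. The text reports 26 patients at the end and 4 drop-outs, and also says that 26 were enrolled. Assuming equal arms, 26 / 2 = 13, or (26 − 4) / 2 = 11.
- True effect: none.
- Shift δ in one arm: 0.25 or 0.5 SD (assumed; the documents give no value).
- Scores: normal with equal variance (assumed). The plan reports p=0.025 against normality for the emotional domain.

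Simulated Mann-Whitney rejection rate, 20,000 trials per setting:

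| Per arm | δ = 0 | δ = 0.25 SD | δ = 0.5 SD |
|---|---|---|---|
| 13 | 4.5% | 8.2% | 20.5% |
| 11 | 4.6% | 7.9% | 18.6% |

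A separate simulation at δ = 0.5 SD gave about 21% (13 per arm) and 19% (11 per arm).

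A closed-form check for a comparison of means uses z = δ / √(2/n) and rejection rate = Φ(z − 1.96) + Φ(−z − 1.96).
- n = 13, δ = 0.5: √(2/13) = 0.392, z = 1.275, rate = Φ(−0.685) + Φ(−3.235) = 24.7%.
- n = 11, δ = 0.5: √(2/11) = 0.426, z = 1.173, rate = Φ(−0.787) + Φ(−3.133) = 21.6%.

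These are somewhat higher, as expected for a normal approximation that treats the SD as known. They agree in order of size.

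**The case against.** **The quoted sentence covers only the baseline form, and attendance at sessions is not stated.** Both are true. A reader might infer that the plan has an unblinded examiner scoring the 6-week MacNew after supervising every session. The documents do not say so, and the flow chart that might assign roles is not in the available text. The point is therefore conditional: the 6-week mode is unspecified, and the only mode described is open to bias.

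**The examiner may simply have written down the patient's own answers.** This is a fair reading. It makes the risk smaller but does not remove it, because the examiner still puts the questions and marks the form, and the patient still answers face to face.

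**The direction of bias is unknown.** A reader might infer that any bias favours the added resistance training. The visible text states no hypothesis. Both groups receive interval training and monitoring, so a patient's wish to please could raise scores in both arms and partly cancel. Only an arm-specific shift produces the rates shown.

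**The illustration says nothing about examiners.** Also correct. Any cause of a one-arm shift would give the same rates. They show what a shift would do in a trial of this size, not that one occurred.

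**Self-completion does not blind the patient.** This stands and limits what the fix can achieve.

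**Conclusion.** The concern holds in conditional form. The plan states that the examiner filled in the baseline MacNew after allocation, and gives no other method, person or blinding for week 6. If the same mode applies at week 6, and the examiner attends the sessions as the ACLS wording suggests, the three 6-week domain scores are open to examiner bias wherever the lottery is placed.

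The size and direction of that bias cannot be established from the documents. The rise from about 5% to about 8% or 19-21% rests wholly on assumed shifts of 0.25 and 0.5 SD, 11 to 13 per arm, normal scores and no true effect.

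This is a weakness in a subjective outcome that should be corrected because the remedy is cheap. It does not show that the MacNew results are wrong.

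**What to change.** Amend the Data Collection Procedure section as follows.

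1. The patient completes the MacNew at baseline and at 6 weeks, away from the examiner, and hands it in sealed.
2. Where reading help is needed, the printed items are read word for word and the patient marks the response. Existing staff who do not know the arm should do this where possible; if the examiner reads the items, the face-to-face influence returns.
3. Each patient uses the same mode at both visits, and the mode is recorded.

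**Cost:** revised wording and a few minutes per patient, with no added staff or tests. Some items will be missed, and some patients will need reading help. A completeness check by someone other than the examiner at hand-in would limit the missed items. Expectation bias remains, because patients know which training they had, and the report should say so.

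**If the visits are already complete**, as the past tense of much of the section suggests, new wording cannot change how the forms were filled in. In that case, report for each visit who completed the form, whether by interview or otherwise, and whether that person knew the arm, and interpret the MacNew comparison as unblinded.

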### **INTEREVNTIONAL GROUP:**

Patients in Interventional group in first set will perform 3 minute of cycling ,1 set of hand grippers 1.5 to 2.5 lbs (10 to 12 reps) and 1 set of biceps resistive exercises 1 Kg to 3 kg (10 to 12 reps) followed by 3minute of pause. In second set patient will perform 3 minutes of stationary cycling , 1 set of quadriceps resistive exercises 1 to 3 Kg (10 to 12 reps) again followed by 3 minutes of pause and in third set patient will perform 3 minutes of treadmill walk at 1.5 to 4 speed, and 1 set of standing ankle pumps (10 to 12 reps).

Patients in both groups will perform cool down exercises that include again breathing exercises, stretching and active exercises. Post exercise vitals will be recorded in both groups.

Figure 3: Patient performing treadmill as a part of treatment protocol

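### Does giving the warm-up as 15 minutes in one section and 3-5 minutes in another call for a change to the plan?

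*Combined protocol and SAP*

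**What the plan says.** The combined protocol and SAP mentions the warm-up in two places.

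- Under DATA COLLECTION PROCEDURE, in the past tense: "Before treatment session proper warm up for 15 minutes was done". The content of those 15 minutes is not given. The recording of pre-session vitals is mentioned straight afterwards. The same section sets the schedule: "Total weeks of treatment session were 6" and "Exercise was performed 3 times a week on alternating days. Total days of exercise were 18".
- Under TREATMENT PROTOCOL, in the future tense: "Treatment of both groups will start with 3-5 minutes of warm up that includes breathing exercises and stretching of major large muscles". Here vitals are recorded before the treatment protocol begins, so they come ahead of this warm-up.

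The section on the interventional group closes with the cool-down for both arms: "Patients in both groups will perform cool down exercises that include again breathing exercises, stretching and active exercises". Figure 2, captioned "Flow chart showing Data collection procedure", is not visible in the text under review and may bear on the point. Its absence is not counted against the plan. No visible sentence links the two durations, calls them separate components, or reports a departure from an intended duration.

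**The concern.** The two durations do not overlap: the longer is three to five times the shorter. Both stand in current text, so neither can be dismissed as superseded wording.

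The gap is also not small beside the session itself. From the group descriptions, controls do three 6-minute bouts, which is 18 minutes of active work. The interventional group does three 3-minute aerobic bouts, which is 9 minutes, plus untimed resistance sets. A gap of 10-12 minutes is more than half of the first figure and exceeds the second.

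What would be at stake is the definition of the session given to post-MI patients. A reader who wished to repeat the programme could not tell how long it began with preparatory exercise. If the two sections record plan and conduct respectively, a departure from plan may have gone unreported. Had the warm-up differed by arm, it would also have become part of the treatment contrast.

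**Working it through.** **Inputs, all from the document.** Warm-up of 15 minutes, 6 weeks, 3 sessions a week and 18 exercise days come from DATA COLLECTION PROCEDURE. Warm-up of 3-5 minutes in both groups comes from TREATMENT PROTOCOL.

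**The plan's own figure.** Sessions = weeks × sessions per week = 6 × 3 = 18, which agrees with the stated 18.

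**Reading A: one warm-up, two rival durations.**

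- Difference per session: 15 − 5 = 10 to 15 − 3 = 12 minutes.
- Per week: 3 × 10 = 30 to 3 × 12 = 36 minutes.
- Total warm-up over 18 sessions at full attendance: 15 × 18 = 270 minutes, against 3 × 18 = 54 to 5 × 18 = 90 minutes.
- Difference over 18 sessions: 270 − 90 = 180 to 270 − 54 = 216 minutes.

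**Reading B: two successive components.**

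- Per session: 15 + 3 = 18 to 15 + 5 = 20 minutes.
- Over 18 sessions: 18 × 18 = 324 to 20 × 18 = 360 minutes.
- Conflict between the sections: none.

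**Which reading does the text favour?** It does not settle the matter.

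- *Placement.* One section puts its warm-up ahead of the session; the other makes its warm-up the opening of treatment. Read literally, these are different moments.
- *Order of vitals.* The first section mentions warm-up and then vitals; the second has vitals and then warm-up. The sequence of 15-minute warm-up, vitals, 3-5 minute warm-up satisfies both. A single warm-up would need a second discrepancy, in order as well as duration. This is suggestive only, because the first section is loosely punctuated at that point and may not be strictly chronological.
- *Tense.* Past against future hints at conduct against plan, but TREATMENT PROTOCOL itself mixes tenses, so this is a poor guide.
- *Cool-down.* That the cool-down repeats breathing exercises and stretching says nothing about how many warm-ups came before the exercise.

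**Does either reading reach the comparison?** TREATMENT PROTOCOL applies its warm-up to both groups, and DATA COLLECTION PROCEDURE makes no distinction by group. As described, the difference between arms in warm-up time is zero under A and under B. The groups are to be compared with the Mann-Whitney U test on vitals, ejection fraction, lipids and the quality-of-life domains (CURVES OF NORMALITY). None of these takes warm-up time as an input, and no sample size, power or alpha figure depends on it. The 180-216 minute total is correct arithmetic, but nothing in the plan uses it.

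**The case for a change.** The strongest case for acting is that the text needs an edit on every reading. With one warm-up, one figure is wrong. With two components, the plan omits to say so and gives no content for the longer one. If the sections are plan and conduct, a departure should have been reported. The edit is cheap, and a component with two unreconciled durations cannot be reproduced with confidence.

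The order of vitals adds something to this. Heart rate recorded after a 15-minute warm-up is not the same quantity as heart rate recorded before any exercise, and vitals are among the variables compared. The text does not say whether the baseline vitals under CURVES OF NORMALITY are these pre-session readings.

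Much of this stands as a comment on description. The ambiguity is real, and the two sections must be reconciled. What does not stand is the step from there to a change of plan. The exercise bouts and resistance sets that separate the arms are specified elsewhere and are unaffected. The vitals order, whatever it was, is given without distinction by group, so it offers no route to bias between arms. Treatment delivery is described largely in the past tense, and post-tests and analysis wholly so; a new specification could no longer alter what patients received. A check of delivered warm-up time also presumes that it was recorded, whereas the text mentions recording only vitals, exertion and fatigue.

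**Conclusion.** No change to the design or analysis follows. The plan describes the warm-up in two unreconciled ways. If they are one warm-up, the gap is 10-12 minutes per session (180-216 minutes over 18 sessions at full attendance). If they are two components, there is no conflict. A true contradiction is not established, and the missing flow chart might settle it.

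The consequence is limited to an ambiguous warm-up description for anyone repeating the programme. Reconciling the two sections, either as one specification or as two named components, is a descriptive edit that leaves the randomised comparison and its conclusion where they were. Which duration is right cannot be decided from the document, and none is preferred here.

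This rests on one assumption that the text supports but cannot prove: that both groups were warmed up in the same way. Evidence that they were not would reopen the point.
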